## 1.2 STUDY FLOW CHART FOR THE DOUBLE-BLIND TREATMENT PERIOD

Week (W) a	Baseline		Treatment period																		Post drug elimination follow up		Unscheduled
	W-4	Rand b	W4	W8	W12	W16	W20	W24	W30	W36	W42	W48	W54	W60	W66	W72	W78	W84	W90	W96/ EOT	EOT +2W	EOT +4W	Relapse visit v
Visit number	1	2	3	4	5	6	7	8	9	10	11	12	13	14	15	16	17	18	19	20 c	21 d	22 d	
Entry procedures																							
Informed consents e and assent	X																						X e
Review inc/excl criteria	X	X																					
Demographics	X																						
Medical/surgical history	X																						
Tuberculosis test s	X																						
Prior medications	X	X																					
Randomization		X																					
Efficacy																							
EDSS	X	X						X			X					X				X			X p
SDMT		X						X			X					X				X			
Cognitive Battery Test u		X																		X			
Brain MRI q	X f							X			X					X				X			

Week (W) a	Baseline		Treatment period																	Post drug elimination follow up		Unscheduled	
	W-4	Rand b	W4	W8	W12	W16	W20	W24	W30	W36	W42	W48	W54	W60	W66	W72	W78	W84	W90	W96/ EOT	EOT +2W	EOT +4W	Relapse visit v
Visit number	1	2	3	4	5	6	7	8	9	10	11	12	13	14	15	16	17	18	19	20 c	21 d	22 d	
Safety																							
Adverse event reporting g		<----->																					
Vital signs h	X	X	X	X	X			X		X		X		X		X		X		X	X	X	X
Physical examination f	X	X			X			X		X		X		X		X		X		X	X		
ECG 12-leads		X																		X	X r	X r	
Tanner i		X						X				X								X			
Clinical routine laboratories k,j	X	X	X		X			X		X		X		X		X		X		X			
Clinical safety laboratories j,l,o				X		X	X		X		X		X		X		X		X		X	X	
Immunoglobulins / TSH		X						X				X								X			
Treatments																							
Concomitant medications		<----->																					
Dispense study drugs/IVRS call		X		X	X			X		X		X		X		X		X		X v			
Accountability / compliance				X	X			X		X		X		X		X		X		X			
Teriflunomide PK sampling m			XXX	X	X			X		X										X	X n	X n	

EOT = end of treatment (EOT= First visit after last study drug intake), EDSS = expanded disability status scale, FS = functional score, BVMTR = brief visuospatial memory test-revised, SDMT=symbol digit modalities test, MRI = magnetic resonance imaging, PK = pharmacokinetic

- a Recommended windows: The window for obtaining biological samples at any given visit will be ±7 days. All other treatment period assessments should be completed within ±7 days of the scheduled visit date relative to the randomization visit. Post drug elimination follow-up visits should be ±7 days of scheduled visit relative to end of treatment.
- b Randomization visit up to 28 days from signing of informed consent.
- c End-of-treatment and premature discontinuation visit. This visit does not need to be performed when the patient switches to the open label period after a confirmed relapse or high MRI activity (as per protocol criteria). The drug elimination procedure must be initiated at this visit if applicable.

- d* For discontinuing treatment, 2 post drug elimination follow up visits should be scheduled 2 weeks and 4 weeks after study medication discontinuation and initiation of the drug elimination procedure. All patients who prematurely and permanently discontinue study medication will be asked to continue until the planned end of double-blind period.
- e* Re-consent must follow any RAP confirmed MS relapse for continuing in study when occurrence during PK run-in, for switching into open-label period when occurrence after PK run-in.
- f* To be prescribed at Visit 1 and report checked at Visit 2. MRI scan performed within 6 weeks prior to randomization can be used as the baseline MRI if performed according to the operations manual and accepted by the central reader.
- g* During the adverse event reporting process, specific questions about pulmonary symptoms and peripheral neuropathy symptoms will be asked. (Patients will be instructed to alert the treating physician of symptoms suggestive of immunodeficiency).
- h* Including systolic and diastolic blood pressure, heart rate, body temperature, weight and height (Height only at V2 and EOT); patient standing in bare or stocking feet. Height and weight is to be documented in the growth charts –Blood pressure (BP) and heart rate to be measured in both the supine and the standing positions (measures taken 3 minutes after supine and 3 minutes after standing). A sphygmomanometer with a blood pressure cuff appropriate to the patient's arm girth is used.
- i* Tanner stage to be assessed at baseline, every 24 weeks and at EOT for all patients (until complete sexual maturity).
- j* Pancreatic ultrasound must be performed if there are clinical or lab abnormalities suggesting pancreatitis or enzymes elevation  $\geq 3$  x ULN and must be followed up with a computed tomography (CT) with contrast or MRI in case of ultrasound with abnormal pancreatic findings
- k* The following routine parameters will be measured at screening, randomization, Weeks 4, 12, 24, 36, 48, then every 12 weeks and at EOT: Hematology and differential panel (hemoglobin, hematocrit, red blood cell count and red blood cell morphology, mean corpuscular volume, white blood cell count, neutrophils, lymphocytes, monocytes, eosinophils, basophils, platelets); Coagulation panel (prothrombin time, and activated partial thromboplastin time); Complete chemistry panel (glucose, creatinine, blood urea nitrogen (BUN), sodium, potassium, chloride, bicarbonate, magnesium, calcium uric acid, aspartate aminotransferase (AST), alanine aminotransferase (ALT), gamma-glutamyl transpeptidase (GGT), lactate dehydrogenase (LDH), total bilirubin, direct/indirect bilirubin, alkaline phosphatase, inorganic phosphorus, total protein, albumin, globulin, albumin/globulin ratio, triglycerides, cholesterol and creatine phosphokinase (CPK). Pancreatic enzymes (serum amylase and lipase); Urinalysis (pH, ketones, protein, glucose, blood, urobilinogen, bilirubin, microscopic sediment, specific gravity). For pubescent females serum pregnancy test  $\beta$ - Human chorionic gonadotropin; ( $\beta$ -HCG) will be performed at screening, randomization and then every 12 weeks
- l* The following safety laboratory tests will be conducted in between clinical routine lab at Weeks 8, 16, 20, 30 and then every 12 weeks up to the end of the study (EOT). Study nurse visit at patient's home can be provided (except at Week 8). In addition at EOT+2 weeks and EOT+4 weeks. The following safety laboratory testing will be conducted: (measuring hematology and differential panel [as above], liver function tests [ALT, AST, GGT, total bilirubin, and direct/indirect bilirubin] and pancreatic enzymes [serum amylase and lipase]). In addition, uric acid and inorganic phosphorus will be done at EOT+2 weeks and EOT+4 weeks.
- m* PK samples will be collected at Week 2, 3, and 4 (PK run-in (8 weeks) period); an additional 4th sample may be required in case of inadequate sampling or information/variability from 3 samples. Study nurse visit at patient's home can be provided when PK sampling is not synchronized with routine lab visit (W2, W3 or in the event the 4th sample is needed).
- n* Post drug elimination procedure sample to be collected for verification of plasma teriflunomide concentrations  $\leq 0.02$   $\mu\text{g/mL}$
- o* In addition if a patient has a vaccination, antibody titers will be assessed before and after vaccination (inactivated vaccines only)
- p* EDSS required also after each clinical relapse, to be performed within 7 days.
- q* If patient is treated with steroids the MRI should be performed after 14 days discontinuation of the steroids
- r* ECG should be performed only for patients who had new abnormalities on the EOT ECG
- s* A tuberculosis test should be performed at screening. An additional test should be performed during the study if deemed clinically indicated. Skin test or blood testing are allowed
- t* The date of first menarche should be captured if applicable
- u* Cognitive Battery Tests: TMT-A and B, SRT, Beery visual-motor integration (BVMI), D-KEFS Fluencies (Letter and Category); BVMT-R and WASI Vocabulary potentially supplemental. When available
- v* IVRS only if treatment is stopped

Please refer to [Section 9.11.4](#) for details.

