### 10.1 VISIT SCHEDULE

It is preferred that all study visits take place in the morning. Visits can be performed on 2 consecutive days when convenient. If a patient is prematurely discontinued from the study treatment, all EOT visit procedures should be performed.

The visit schedule consists of the following visits:

- Screening (Visit 1/Week -4) up to 4 weeks prior to the randomization visit (Visit 2).
  - No IMP is administered in this period.
- Double-Blind Treatment period
  - Randomization (to either teriflunomide or placebo) at randomization (Visit 2),
  - Patients will be on the treatment period of the study for 96 weeks unless prematurely discontinued or switching to the open-label extension period,
  - Patients experiencing a relapse after the PK run-in period (8 weeks) and if confirmed by the Relapse Adjudication Panel (RAP) will have the option to continue in an open label teriflunomide treatment arm. If RAP does not confirm the relapse, the patient may continue in the double-blind treatment period or prematurely discontinue treatment,
  - Visit 3 (W4) to Visit 20 (W96/EOT),
  - For patients prematurely discontinued from treatment, Visit 20 (W96/EOT) procedures should be performed,
  - Clinical laboratories are performed in both routine study site visits and safety laboratory visits that are performed locally (see [Section 1.2](#); two separate lines in the flowchart to indicate the different schedules),
  - In case of at least 5 new/enlarged T2 lesions at the MRI of Week 24, an additional MRI will be performed at Week 36. Then, in case of -at least 9 new/enlarged T2 lesions at Week 36 or -at least 5 new/enlarged T2 lesions on each of the 2 consecutive MRI scans of Week 36 and Week 48, or at least 5 new/enlarged T2 lesions on each of the 2 consecutive MRI scans of Week 48 and Week 72, patients will have the option to continue in the open label period.
- Post drug elimination follow up period (4 weeks)
  - No IMP is administered in this period,
  - Patients who complete the treatment period as well as patients who discontinue prematurely should be scheduled for 2 follow-up visits (Visit 21 and Visit 22),

- Patients will be taking non-IMP (either cholestyramine or activated charcoal) to accelerate the drug elimination process, starting immediately after IMP discontinuation (ie, the same day or the day after).

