#### **11.4.5 Analyses of safety data**

The summary of safety results will be presented by treatment group. Analysis of safety will be performed using the safety population. Safety data in patients who do not belong to the safety population (eg, exposed but not randomized) will be listed separately, as appropriate.

The safety analysis will be based on the reported AEs and other safety information including clinical laboratory data, vital signs and ECG data. The baseline value is defined as the last available value before the first intake of IMP.

The observation periods for safety during the 96-week double-blind period will be as follows:

- Screening Period is from informed consent to first dose of IMP.
- Treatment-emergent adverse event (TEAE) period is defined as from first dose of IMP up to 4 weeks (28 days) after last dose of IMP or up to inclusion in open label treatment phase, whichever occurs first. The TEAE period can be divided into 2 distinct periods:
  - Treatment Period from first dose of IMP to last dose of IMP,
  - Accelerated elimination period from 1 day after treatment period up to 4 weeks (28 days) after last dose of IMP or up to inclusion in open label treatment phase, whichever occurs first.

- The post-treatment period is from the day after the TEAE period to the end of the 96-week double-blind period, where applicable.

All safety analyses will adhere to sanofi “Guideline for the Analysis and Reporting of Safety Data from Clinical Trials”.

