2.1.4 Safety endpoints

The safety analysis will be based on the reported adverse events and other safety information, such as clinical laboratory data, vital signs, ECG, etc.

Observation period

The observation period of the open-label period will be divided into 3 epochs:

- The **treatment** epoch is defined as the time from the first administration of the IMP in the open-label period to the last administration of the IMP in the open-label period.
- The **accelerated elimination** epoch is defined as the time from 1 day after the open-label treatment epoch up to 4 weeks (28 days) after the last administration of the IMP in the open-label period or up to the first administration in optional additional extension period, whichever occurs first.

The treatment-emergent adverse event (TEAE) period will include both treatment and accelerated elimination epochs.

- The **posttreatment** epoch is defined as the period of time starting from the day after the end of the treatment-emergent adverse event period up to the end of the open-label period (defined as the first dose of optional additional extension IMP for patients enter optional additional extension period, or the last protocol-planned visit, EOT +4W, in the open-label period or the resolution/stabilization of a followed-up AE for patients do not enter).

The on-study observation period is defined as the combination of TEAE period and posttreatment epoch.

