2.4.5 Analyses of safety data

The summary of safety results will be presented by treatment patients actually received in the double-blind and open-label period (placebo/teriflunomide and teriflunomide/teriflunomide) and overall treatment group. Baseline values of the double-blind period will be used as the baseline in the safety analysis for the open-label CSR, unless otherwise noted.

General common rules

All safety analyses will be performed on the safety population as defined in [Section 2.3.3](#), unless otherwise specified, using the following common rules:

- Safety data in patients who do not belong to the safety population will be listed separately.
- The baseline value is defined as the last available value before the first intake of IMP in the double-blind period.
- The potentially clinically significant abnormality (PCSA) values are defined as abnormal values considered medically important by the Sponsor according to predefined criteria/thresholds based on literature review and defined by the Sponsor for clinical laboratory tests, vital signs, and ECG (PCSA version dated May 2014 [[Appendix A](#)]).
- PCSA criteria will determine which patients had at least 1 PCSA during the treatment-emergent adverse event period, taking into account all evaluations performed during the treatment-emergent adverse event period, including nonscheduled or repeated evaluations. The number of all such patients will be the numerator for the on-treatment PCSA percentage.
- The treatment-emergent PCSA denominator by group for a given parameter will be based on the number of patients assessed for that given parameter in the treatment-emergent adverse event period by treatment group on the safety population.
- For quantitative safety parameters based on central laboratory/reading measurements, descriptive statistics will be used to summarize results and change from baseline values of the double-blind period by visit and treatment group. Summaries will include the endpoint value and/or the minimum and maximum value. The endpoint value is commonly defined as the value collected at the same day/time of the last administration of IMP in the open-label period. If this value is missing, this endpoint value will be the closest value prior to the last dose intake.

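### The treatment-emergent window closes 28 days after the last dose, but the last planned safety visit is centred on or after that day, so about half of its permitted dates (at a 0 to 1 day EOT lag) fall outside the period in which most PCSAs are counted

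*Protocol*

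**What the plan says.** **When the last safety visit happens.** The definitions under the protocol 1.2 flow chart read: "EOT = end of treatment (EOT= First visit after last study drug intake". The flow chart places the two post-elimination visits at EOT+2W and EOT+4W, and footnote a sets the tolerance: "Post drug elimination follow-up visits should be ±7 days of scheduled visit relative to end of treatment". Footnote c, on the EOT visit, says: "The drug elimination procedure must be initiated at this visit if applicable". Other passages use a different anchor. Footnote d has the visits "scheduled 2 weeks and 4 weeks after study medication discontinuation and initiation of the drug elimination procedure", section 10.1.4 agrees with it, and section 10.1 has washout "starting immediately after IMP discontinuation (ie, the same day or the day after". Protocol Table 3 lists the EOT pharmacokinetic sample as pre-dose.

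**When the window closes.** Protocol 11.4.5 runs the TEAE period "up to 4 weeks (28 days) after last dose of IMP or up to inclusion in open label treatment phase, whichever occurs first". SAP 2.1.4 runs the accelerated elimination epoch "up to 4 weeks (28 days) after the last administration of the IMP in the open-label period", or to the first optional-extension dose if that is earlier. The posttreatment epoch follows, and EOT+4W is named there as one of its possible ends.

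**What is collected.** Protocol 10.1.4 schedules vital signs, haematology, liver tests, pancreatic enzymes, uric acid and inorganic phosphorus at both visits.

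**What is counted.** SAP 2.4.5 states: "PCSA criteria will determine which patients had at least 1 PCSA during the treatment-emergent adverse event period". Protocol 11.4.5 and SAP 2.4.5.3 and 2.4.5.4 limit the laboratory and vital-sign incidences in the same way. SAP 2.4.5.3 gives parameters without PCSA criteria similar tables based on the normal range. The liver tables in both documents instead cover any post-baseline visit. For the posttreatment epoch, SAP 2.4.5.1 plans adverse event tables only.

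**The concern.** The window is tied to a dose date and the visit to a visit date (or, in some passages, to discontinuation). The window allows exactly 28 days, with no room for the visit tolerance. Two children with the same abnormal result at the same planned visit can therefore be treated differently. The one seen on day 28 is counted and the one seen on day 29 is not.

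A child with earlier on-treatment samples stays in the PCSA denominator either way, because SAP 2.4.5 bases it on being assessed during the TEAE period. A late abnormal result can then only be missing from the numerator. These are the last planned safety results in children coming off the drug, some of whom stop because of cytopenia or raised enzymes (protocol 10.3.2.1).

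**Working it through.** **Inputs**
- Window: 4 weeks after the last dose, 4 × 7 = 28 days, which reproduces the stated figure. Day 28 counts as inside.
- Visit: EOT + 28 days, k = −7 to +7 days, so 15 permitted days (1.2, footnote a).
- L: days from last dose to EOT. The documents give neither a value nor a maximum.

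**Step 1: share of EOT+4W days outside.** The visit falls on day L + 28 + k after the last dose. It is outside when L + 28 + k > 28, that is k > −L. This leaves 7 + L of the 15 days, up to a maximum of 15.

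| L (days) | Target day | Days outside | Share |
|---|---|---|---|
| 0 | 28 | 7 of 15 | 46.7% |
| 1 | 29 | 8 of 15 | 53.3% |
| 3 | 31 | 10 of 15 | 66.7% |
| 7 | 35 | 14 of 15 | 93.3% |
| 8 or more | 36 or later | 15 of 15 | 100% |

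These are shares of permitted days. They become shares of samples only if visits spread evenly over the window, and neither document gives a distribution. With a triangular spread (weight 8 − |k|, total 64) the shares are 28/64 = 43.8% at L = 0 and 36/64 = 56.2% at L = 1. If every visit is exactly on target, L = 0 is inside (day 28) and any L of 1 or more is outside.

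**Step 2: which L the text supports.** Section 10.1 (washout on the day of stopping or the next), read with footnote c (washout started at EOT), gives L of 0 or 1. Dating the visits from discontinuation (footnote d, 10.1.4) gives the L = 0 row if that is the last-dose day. The pre-dose EOT sample in Table 3 suggests a dose on the EOT day (L = 0). If EOT follows the last morning tablet, as 1.2 defines it, L = 1.

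**Step 3: the EOT+2W visit.** Its latest permitted day is 14 + 7 + L = 21 + L, which is inside for L up to 7.

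**Step 4: the washout course.** Eleven days started at EOT or the day after end by day L + 11, which is inside for L up to 17.

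**Step 5: where a result after day 28 goes.**
- Haematology, pancreatic enzymes, uric acid and vital signs: the PCSA incidence is limited to the TEAE period, so they are not counted.
- Inorganic phosphorus: SAP Appendix A has no criterion, so it falls to the normal-range table, which follows the same rule.
- Liver tests: not in the general incidence, but eligible for the any-post-baseline tables (protocol 11.4.5, SAP 2.4.5.3).
- By-visit summaries: the double-blind window stops at last dose + 28 days (SAP Table 6, footnote c). The open-label window runs to the last open-label visit (Table 7, footnote c), but only the value closest to target is used.

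**The case against.** The strongest reply is that closing at last dose + 28 days is a deliberate definition: SAP 2.1.4 itself places EOT+4W at an end of the posttreatment epoch. Late results also remain visible elsewhere. Patients with a post-baseline PCSA are listed with their full profile, clinically significant abnormalities are reported as adverse events with a causality assessment (protocol 9.10.2.1), and posttreatment adverse events are tabulated. The safety analysis is essentially descriptive. All of this stands, but none of it returns the results to the incidence counts.

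A reader might infer more than the text supports:
- *Most EOT+4W samples are lost.* This needs L of at least 1 day, which is not stated; at L = 0 the share is just under half. Longer lags are foreseeable, since early stoppers perform EOT procedures if possible (10.3.2.2) and Appendix G allows visit windows to be extended, but no figure is given.
- *Late results enter no PCSA table at all.* This is wrong for liver tests. SAP 2.4.5.3 also tabulates post-baseline ALT thresholds and normalization after IMP discontinuation.
- *Washout itself falls outside its epoch.* The 11-day course stays inside unless the lag exceeds 17 days.
- *Everything is dated from EOT.* That is one of several conflicting wordings.

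The scope is also limited. Patients entering open label have the window closed at entry, and those going straight to commercial product skip these visits. The double-blind analysis has its own SAP, which is not among the documents.

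**Conclusion.** The point holds in a limited form. The TEAE period and accelerated elimination epoch do not cover the tolerance of the last planned safety visit. At the lag the text best supports (0 to 1 day), 47% to 53% of that visit's permitted days lie outside. The share reaches 100% at 8 days or more, but the documents state no such lag.

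The consequence is confined to patients who stop teriflunomide, and to the haematology, pancreatic enzyme, uric acid, phosphorus and vital-sign incidence tables, with liver tests partly protected. The number of patients and abnormal results affected cannot be derived from the documents. The percentages count calendar days and describe samples only under an assumed spread of visits. The change is worth making before the tables are programmed; it does not bear on efficacy.

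**What to change.** In protocol 11.4.5 and SAP 2.1.4, end the accelerated elimination epoch and the TEAE period at the later of last dose + 28 days and the EOT+4W visit date, still truncated at the first dose of the next period. Start the posttreatment epoch on the following day, and align footnote c of SAP Table 6. Check the separate double-blind SAP for the same derivation. A fixed extension to last dose + 35 days would capture every permitted visit only when L = 0, so the end should follow the visit date.

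The passages on the EOT definition, the EOT pre-dose sample, washout start and the anchor for the follow-up visits (protocol 1.2 definition and footnotes a, c and d; Table 3; 10.1; 10.1.4) must also be reconciled. No clinical rule is proposed here.

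The cost is one date derivation plus wording. A few more days, and any events in them, would count as treatment-emergent. Window length would vary slightly with attendance, staying at 28 days for a missed visit.
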